Aim 2. Imaging functional correlates of alcohol analgesia. Empirical data regarding neural correlates alcohol analgesia are needed to inform models proposing common substrates underlying pain and acute/chronic alcohol effects (e.g., Egli et al., 2012). Unlike other analgesics (e.g., mu-opioid agonists), alcohol acts on most major neurotransmitter systems. However, no studies have examined neural mechanisms underlying alcohol analgesia. Regions of interest (ROIs) include brain structures underpinning discriminative, affective, and cognitive components of the pain experience, including anterior/posterior cingulate cortices, thalamus, insula, somatosensory cortices, hypothalamus, amygdala, and medial/dorsolateral prefrontal cortex. These regions are also implicated in addiction (Egli et al., 2012) and are vulnerable to disruption following acute alcohol administration (e.g., Anderson et al., 2011; Marinkovic et al., 2012, 2013). Thus, we predict **H5**. that alcohol administration will be associated with disruption of BOLD activation and functional connectivity in/between regions associated with the affective and cognitive aspects of pain processing (e.g., insula, prefrontal cortices, amygdala, nucleus accumbens) during application of heat pain stimuli. Based on our pilot data, we expect **H6**. FH+ individuals will demonstrate more severe alcohol-related functional disruption in these ROIs, including motivation-related circuits implicated in transition to chronic pain (Baliki et al., 2011).

Aim 3. Test sex as a moderator of alcohol and FH effects. On the basis of our pilot data, as well as studies of sex differences on the efficacy of opioid analgesics (Fillingim and Gear, 2004; Niesters et al., 2010), we expect **H7**. women will experience greater reductions in pain sensitivity as a result of alcohol consumption and report greater feelings of relief compared to men. We ask as **Empirical Question 1**. whether sex will serve as a moderator of the effect of FH of alcoholism on alcohol analgesia and its functional neural correlates. Evidence of sex by FH interactions may help to identify subgroups at particular risk for harm from self-medication of pain with alcohol.

6. Research Plan:

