Resting-State Scanning. First, participants will complete two resting-state (i.e., task-free) scans while keeping their eyes open and focused on a fixation cross. Resting-state fMRI is a powerful tool used to elucidate large- scale neural networks underlying human brain architecture (Biswal et al., 2010). Of these intrinsic connectivity networks, the subcortical limbic network is most relevant to the current project. Although previous studies have examined this resting-state network in the context of heroin (Schmidt et al., 2015) and tobacco (Janes et al., 2012) dependence, intrinsic connectivity of this network has yet to be explored in the context of acute alcohol effects. This project will use a resting-state fMRI protocol to examine differences in subcortical limbic system connectivity (as well as other pain- and reward-related resting state networks) between groups at baseline, as well as between conditions to determine whether acute alcohol consumption differentially disrupts this network in individuals with a family history of alcoholism. One resting state scan will use a conventional BOLD-sensitive T2* weighted sequence. The other will use a partial-continuous arterial spin labeling (pCASL) sequence because these scans yield estimates of cerebral blood flow (CBF) which can be used as covariates in BOLD analysis of subsequent task-based scans, accounting for the cerebrovascular effects of alcohol administration (Marinkovic et al., 2013). Each resting state scan will require approximately 9 minutes.

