H5, that alcohol administration will be associated with disruption of BOLD activation in/between regions associated with affective and cognitive aspects of pain processing during application of heat pain stimuli, and H6, that this disruption will be stronger among FH+ individuals, especially within motivation-related structures/circuits, will be evaluated using a two-part process. For all analyses described, motion will be controlled for at the individual subject level (i.e., first level) by including all six movement parameters (x/y/z translation, pitch/roll/yaw) and outlier volumes (determined using the Artifact Reduction Toolbox) as nuisance covariates. We will also co-vary for mean cerebral blood flow measured using pCASL-based resting state scans. Familywise error will be controlled for all analyses using false discovery rate correction (FDR; Benjamini and Hochberg, 1995) at $p < .05$.

Resting-state analyses: Pre-processed resting-state data will be analyzed using hybrid ICA-seed-based fcMRI analyses (Kelly et al., 2010). For this approach, independent components analysis (ICA) and seed- based correlations are used in tandem. First, ICA will be used to empirically derive a priori regions of interest (ROIs) based on resting-state networks identified from the study's participants. Networks of particular interest in this study include those associated with processing of nociceptive stimuli and those that

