are disrupted in chronic pain, including default mode network (DMN), salience network (SN), executive control network (ECN), and subcortical limbic network (LN) (Martucci and Mackey, 2016). ICA will be conducted using the voxel-to- voxel processing stream in the CONN toolbox, which involves back-projection of ICs identified across subject and condition to identify spatial components, followed by back-projection of these components to individual subjects (Calhoun et al., 2001). ICs most closely matching networks of interest will be identified based on masks derived from NeuroSynth (Yarkoni et al., 2011). Second, seed-based fcMRI analyses will examine Fishers' r-to-z transformed correlations between the ICA-derived seed ROIs and all other voxels in the brain. Seed-based correlation analyses will be conducted in the Conn Toolbox (Whitfield-Gabrieli & Nieto-Castanon, 2012). Hybrid ICA-seed-based fcMRI has been shown to yield accurate and reproducible results (Franco et al., 2013; Kelly et al., 2010). We will examine interactions of group and condition on connectivity of these resting-state networks using repeated measures GLM, followed by simple main effects decomposition.

Task-based analyses: Alcohol-related changes in BOLD activity in pain- and reward-related brain structures during painful stimulation will be evaluated using a GLM-based approach in SPM12. Following convolution of the canonical hemodynamic response function with the heat stimulation paradigm at the single subject level, group-level effects of dose, sex, and FH on pain-related activations in ROIs and in whole brain will be assessed. To examine the changes in functional connectivity associated with alcohol analgesia, task-based data will be analyzed using the psychophysiological interaction (PPI) pipeline within the Conn Toolbox. PPI is a method of examining task-modulated increases in functional connectivity through GLM by yielding an interaction term (i.e., PPI regressor) from the product of a task's convolved time course (e.g., blocks of noxious thermal stimulation) and the time course from a seed ROI (O'Reilly et al., 2012). Relevant seed ROIs for this analysis will be generated using ICA as described above. We will examine task-dependent functional connectivity in pain- and reward-related networks, both between groups and within conditions, using rmGLM.

Aim 3. Test sex as a moderator of alcohol and FH effects.

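### H5, and H6 as restated in the analysis plan, concern brain activity during heat pain, but one of the two analyses assigned to them uses task-free resting scans, and nothing says which analysis decides

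*Combined protocol and SAP*

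**What the plan says.** Section 5 (Specific Aims, Aim 2) states H5 as disruption by alcohol of activation and functional connectivity "during application of heat pain stimuli". Section 6 (Data Analysis Strategy, Aim 2) keeps the condition: the regions are those "associated with affective and cognitive aspects of pain processing during application of heat pain stimuli". The same sentence restates H6 as this disruption being stronger in FH+ participants, and closes with "especially within motivation-related structures/circuits, will be evaluated using a two-part process".

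Two headed blocks follow.

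- **Resting-state analyses.** "Pre-processed resting-state data will be analyzed using hybrid ICA-seed-based fcMRI analyses". The inference is then stated: "We will examine interactions of group and condition on connectivity of these resting-state networks using repeated measures GLM", with simple main effects to follow.
- **Task-based analyses.** A GLM of BOLD activity during painful stimulation, with effects of dose, sex and FH, plus PPI connectivity during the heat blocks.

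Under Resting-State Scanning, "participants will complete two resting-state (i.e., task-free) scans while keeping their eyes open and focused on a fixation cross". The fMRI Heat Pain Protocol section places the three heat runs after the resting scans. Resting-State Scanning also gives those scans their own purpose: to learn whether alcohol disrupts the subcortical limbic network, and other pain- and reward-related networks, differently in people with a family history.

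**The concern.** A test bears on a hypothesis only if its null contradicts that hypothesis. H5 says that alcohol changes the brain's response to heat pain. The resting-state test has a different null: that connectivity at rest, with no stimulus, does not change with condition differently between groups. Either null can be true while the other is false.

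The plan nevertheless places both tests under H5 and H6 and gives no rule for what happens if they disagree. Suppose resting connectivity shifts under alcohol but the response to heat does not. The Aim 2 text does not tell the analyst, or a later reader, whether H5 was supported. The Background says that network changes accompanying alcohol analgesia have never been characterised. A change in resting networks with no pain present would then be open to being presented as a mechanism of pain relief.

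**Working it through.** The document gives no power, sample size or error figure for H5 or H6, so there is nothing of the plan's own to reproduce. The check is a comparison of texts, followed by one illustration.

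**1. What each hypothesis requires.**

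- H5 requires heat in both places where it is stated (Specific Aims; Data Analysis Strategy, Aim 2).
- H6 in the Specific Aims predicts more severe alcohol-related disruption in the listed regions for FH+ and does not itself mention heat.
- H6 in the Data Analysis Strategy refers back to the H5 disruption and so takes on the heat condition.

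**2. What each part measures.**

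| Part | Stimulus during the scan | Stated inference | Bears on H5? |
|---|---|---|---|
| Resting-state | None; fixation cross | Group × condition on resting networks, then simple main effects | No |
| Task-based | Individually calibrated heat blocks | Dose, sex and FH effects on heat-related activation; PPI connectivity | Yes |

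**3. Whether the resting part is only preparatory.** It partly is. The independent components analysis (ICA) described there supplies the seed regions for the heat-task PPI, and the pCASL resting scan supplies the cerebral blood flow covariate. But the block also ends in its own group × condition test on resting connectivity. Neither supporting role needs that test.

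**4. Whether a decision rule exists elsewhere.** For H1 to H4 and H7, the Data Analysis Strategy says what result would be read as support. For H5 and H6 it does not. The plan marks some other analyses as not a primary aim (spectroscopy; rate of rise of blood alcohol), but not the resting-state analyses. The false discovery rate correction addresses multiple testing, and the blood flow covariate addresses vascular effects. Neither makes a resting test informative about heat.

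**5. Illustration of size.** The assumptions are mine: one test per part at .05, independent parts, no true effect in either, and support claimed if either part is significant.

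- Task-based part alone decides: false support = .05.
- Either part suffices: 1 − (1 − .05)(1 − .05) = 1 − .9025 = .0975.

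**The case against.** Four points can fairly be made for the plan.

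- **Nothing says a resting result supports H5.** True. The hypothesis is limited to heat by its own wording, and a careful author would not claim support from rest alone. The either-part rule in the illustration is an assumption. What remains is that the plan lists the resting test as part of the evaluation and is silent on how it counts.
- **The two parts can be read as a sequence:** derive networks at rest, then test them under heat. This is reasonable for the ICA step, which should stay. It does not explain the separate resting-state group × condition test.
- **H6 may be broader than heat.** As worded in the Specific Aims, it could cover resting connectivity. This stands, so the mismatch for H6 rests on the restatement in the Data Analysis Strategy.
- **The task-based analyses test H5 properly.** They do. The problem is an extra test placed under the same hypothesis.

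A reader might go further and infer that any general alcohol effect on resting networks would be reported as support for H5, with a very high false-support rate. The documents do not support that. The resting test they name is an interaction, and an alcohol effect of equal size in FH+ and FH− produces no interaction. Simple effects might expose a general dose effect, but the plan does not say whether they are run when the interaction is not significant. The document also gives no effect size for alcohol or FH on connectivity. The pilot FH effects in the Power Analysis are behavioural and cannot stand in for one.

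**Conclusion.** The point holds as a mismatch between hypothesis and analysis. It is clear for H5: the resting-state group × condition test contains no heat-evoked signal, so neither a positive nor a negative result bears on H5. It is weaker for H6, where it applies to the version in the Data Analysis Strategy. Both conclusions take the two headed blocks to be the two parts of the process. The plan never lists the parts, but no other candidates follow the sentence.

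The size cannot be taken from the documents. The 9.75% against 5% shows only what a second, irrelevant chance of a positive would add under the assumptions stated; it is not an estimate for this study, whose imaging analyses involve many tests under false discovery rate correction. The textual mismatch does not depend on it. The point is worth correcting because it changes what may be concluded from Aim 2 and costs almost nothing to settle.

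**What to change.** In section 6, Data Analysis Strategy, Aim 2:

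1. State that H5 (effect of dose) and H6 as restated there (FH × dose) are decided by the heat-task activation and PPI analyses.
2. Keep the ICA for deriving PPI seeds and the pCASL scan for the blood flow covariate, and describe both as supporting steps.
3. Report the resting-state group × condition results as a separately labelled secondary question, using the purpose already given under Resting-State Scanning, and say that a resting-state result alone does not support H5 or H6.
4. Align the two wordings of H6 so that both say whether heat is a condition.

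The cost is a few sentences. No scan, analysis or participant burden changes. The one loss is that a resting-state finding can no longer be cited as confirming H5 or H6.

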General Approach. For this study of healthy, community-dwelling moderating drinkers, we propose a repeated-measures, double-blind placebo-controlled factorial design with FH of alcoholism (+/-) and sex as between-subjects factors and alcohol administration (Alcohol Dose: placebo, 0.08 g/dL) as a within-subject factor. The study will include equal numbers of men and women. Study procedures will occur in the Center for Pain Research and Behavioral Health of the University of Florida under supervision of the PI (JB). The investigative team, including the PI; Drs. [name], [name], and [name]; and research assistants, will meet on a bi-weekly basis over the course of the project to

ensure successful completion. Recent progress regarding all aspects of the study will be addressed during these meetings, including ongoing review of recruitment practices and behavioral and imaging data quality. Drs. [name], [name], [name], and [name] will also work together to ensure all research assistants are fully trained to conduct the project.

Methods

Participants. Healthy volunteers (N=220; 110 women) will be recruited for the study via flyers, word of mouth, and internet and local radio advertisements with the aim of obtaining 110 completers; 55 women). Individuals aged 21-45 years will be recruited in order to avoid confounding effects of binge-drinking patterns associated with college-aged individuals and the apparent increased susceptibility of older adults to the acute neurobehavioral effects of alcohol (e.g., [name] et al., 2014). We plan to enroll a representative sample of participants from our recruitment area in north central Florida (i.e., 65% white, 23% black, 7% Asian, 5% other), including ~10% identifying as Hispanic or Latino (see targeted recruitment table).

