Selection Criteria. Participants will be excluded if they have a history of chronic pain (e.g., osteo- or rheumatoid arthritis, fibromyalgia, complex regional pain syndrome) or report regular (i.e., > weekly) use of analgesic medications; current major depression, or history of major depressive disorder if electroconvulsive therapy had been used; past diagnosis of any psychotic disorder; undercontrolled hypertension or diabetes (as reflected by self-report); neurological disease (e.g., multiple sclerosis, epilepsy, amyotrophic lateral sclerosis, Parkinson's disease); serious medical illness (e.g., hepatitis, HIV/AIDS); impaired cognitive function; or history of drug or alcohol dependence. Because evidence suggests chronic smoking is associated with adverse changes in brain structure and neurobehavioral function ([name] et al., 2011; Durazzo et al., 2013), participants must be non-smokers. Alcohol naïve individuals will also be excluded. To increase ecological validity and improve feasibility of recruitment, use of prescription and over-the-counter (OTC) medications will be allowed provided they do not contraindicate alcohol use ([name] et al., 2014; Gilbertson et al., 2009).

Screening Procedure. Individuals will complete an initial screen upon contacting the Center for Pain Research and Behavioral Health via phone or email. During the initial screen, the PI or a trained research assistant will describe the study and general entry criteria. Individuals who qualify and remain interested will be scheduled for a formal screening in the laboratory. During this screening session, additional information regarding demographics, personal and FH of drug and alcohol use (including nicotine), affective and personality measures, attitudes about pain, alcohol-related expectancies, and medical history will be collected (see Table 1). Individuals reporting at least one parent with a history of alcohol problems on the FTQ will be considered to have a family history of alcoholism (FH+; Mann et al., 1985). Notably, in addition to measures of typical consumption, the Alcohol Use Questionnaire (AUQ) includes an assessment of

the maximum quantity of alcohol they have consumed in a single setting in the last 6 months. Although not

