FH of alcoholism was associated with greater expectancy of pain relief from alcohol intake in our pilot work ($d = 1.12$), as well as lower ratings of pain relief ($d = .54$). Effects of sex on these measures were large ($d > .88$). Sex also appeared to be a potent moderator of alcohol analgesia ($d > .90$), with women showing stronger analgesic effects. Our sample will provide $> 80\%$ power to detect these effects. FH was associated with smaller effects on alcohol-related reductions in pain intensity ($d = .42$), as well as pain threshold and tolerance ($d < .26$), resulting in $\sim 54\%$ power to detect interactive effects of FH and dose on these measures.

Across participants, preliminary data suggested small-to-moderate correlations between expectancy of pain relief from alcohol, ratings of pain relief, and typical daily drinking and reductions in pain sensitivity ($.26 < r < .44$). We anticipate $\sim 80\text{-}99\%$ power to detect these effects. However, our data also suggested that sex and FH may moderate these relationships. The interaction of sex and expectancy of pain relief strongly predicted increases in pain threshold and tolerance associated with alcohol intake ($f^2 > 1.11$). A similar effect was detected for the interaction of FH and expectancy of pain relief ($f^2 > .81$). A weaker interaction of FH and ratings of relief on QST measures was also detected ($f^2 > .37$). Likewise, interactions of sex with typical daily drinking and ratings of relief showed some relation to QST changes ($f^2 < .21$). We anticipate $> 94\%$ power to detect each of these interactions. There was little evidence of Sex or FH interactions with typical drinking on alcohol analgesia ($f^2 < .04$). Effect sizes of FH X Sex X expectancy/relief/typical drinking interactions could not be assessed given our limited sample; however, we anticipate sensitivity to detect an interactive $f^2 > .14$ with 80% power given our recruitment target.

Data Analysis Strategy. Data will be analyzed using SPSS 24 (IBM Corp., Armonk, NY).

Aim 1. Test competing hypotheses regarding the effects of family history of alcoholism on alcohol analgesia. To assess hypotheses related to Aim 1, FH status will be included as an independent variable in repeated measures general linear models analyses (rmGLM; SPSS GLM procedure; repeated: dose), with pain threshold/tolerance and intensity ratings, associated relief ratings, expectancy of pain

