To evaluate Aim 3, sex will be included as a factor of interest in rmGLM analyses described under Aims 1 and 2. A sex by dose interaction such that alcohol consumption produces greater reductions in pain sensitivity and higher VAS ratings of relief for women than men will provide support for H7. Presence or absence of a significant sex by family history by dose interactions on metrics of alcohol analgesia will inform Empirical Question 1. Sex will also be included as a factor of interest in analyses of functional neuroimaging data to determine whether sex and FH of alcoholism interact to determine the effects of acute alcohol administration on pain-related brain processes.

7. Possible Discomforts and Risks:

Psychological Discomforts and Risks. Some aspects of the questionnaires utilized in this proposal may make study participants uncomfortable, especially those dealing with affect or medical history. To ameliorate this possibility, participants will be informed they

can withdraw from the study at any time or skip individual questions that may be upsetting to them.

Acute Alcohol Intake. Alcohol intake may result in dizziness, nausea, and vomiting should a participant tolerate the active dose of alcohol poorly. The risk of these as well as more serious consequences may increase if a participant uses medications that contraindicate the use of alcohol (e.g. benzodiazepines/opioid analgesics). Should a participant experience any of these symptoms, they will be allowed to rest until symptoms subside and will be allowed to withdrawal from the study if desired. We have attempted to minimize this risk by recruiting only those who are regular moderate drinkers and excluding those regularly taking prescription medications that contraindicate the use of alcohol. Ss will be rescheduled if they report having taken prescription or over-the-counter medications that contraindicate alcohol use on the day of testing.

Pregnancy: Alcohol intake is an unacceptable risk in pregnancy. Therefore, anyone of childbearing potential will be tested for pregnancy on the morning of the laboratory session. Positive pregnancy tests will result in exclusion from study and lab staff will assist in making a referral as appropriate. Finally, any documents associated with a participant testing positive for pregnancy will be destroyed without reference to a specific cause.

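### A non-significant sex by FH by dose term cannot show that moderation is absent: with 110 completers the 95% interval is about ±0.76 SD, and no power is stated for this term

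*Combined protocol and SAP*

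**What the plan says.** All references are to the combined protocol and SAP.

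- Section 5, Aim 3 asks, as Empirical Question 1, whether sex moderates the FH effect on alcohol analgesia, and gives the reason: "Evidence of sex by FH interactions may help to identify subgroups at particular risk for harm from self-medication of pain with alcohol".
- Section 6, Data Analysis Strategy, Aim 3 gives the basis for answering: "Presence or absence of a significant sex by family history by dose interactions on metrics of alcohol analgesia will inform Empirical Question 1". No other basis is named for the pain measures.
- Section 6, General Approach sets the design, with "FH of alcoholism (+/-) and sex as between-subjects factors and alcohol administration" as the within-subject factor, and adds: "The study will include equal numbers of men and women".
- Section 6, Participants: "Healthy volunteers (N=220; 110 women) will be recruited for the study", "with the aim of obtaining 110 completers; 55 women". The Power Analysis works from the 110 completers.
- Section 6, Screening Procedure classifies FH from the questionnaire ("Individuals reporting at least one parent with a history of alcohol problems on the FTQ will be considered to have a family history of alcoholism") but fixes no ratio of FH+ to FH-.
- Section 6, Power Analysis: "FH was associated with smaller effects on alcohol-related reductions in pain intensity" (d = .42), with d below .26 for threshold and tolerance, and about 54% power for FH by dose. Its one three-way sensitivity figure (f² above .14 at 80% power) is for FH by sex by expectancy, relief or typical drinking, not for sex by FH by dose.

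**The concern.** A non-significant interaction supports absence only if the study could have detected, or its interval can exclude, a difference worth knowing about. The three-way term compares the FH effect in women with the FH effect in men. With four cells of about 27 people, its standard error is twice that of the FH by dose effect, for which the plan already concedes about 54% power. The plan nevertheless treats both outcomes of the significance test as informative, without saying how large a sex difference could go unseen.

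At stake is what the trial may say about sex-specific risk. Aim 3 offers this interaction as a way to find subgroups at particular risk. A non-significant term reported as absence could be taken to mean that FH matters equally in men and women, when the data would also be compatible with large differences.

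**Working it through.** **Inputs from the document.** 110 completers, 55 of them women; FH by sex between subjects, two dose levels within subject; two-tailed tests; pilot FH effects on alcohol-related change of d = .42 (intensity) and d < .26 (threshold, tolerance), reported for FH without separation by sex.

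**Assumptions, not in the document.** Equal FH split within each sex, so 110/4 = 27.5 per cell; alpha .05 per metric for these models; d in units of the alcohol-minus-placebo change-score SD, equal across cells.

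**1. The plan's nearest figure.** With two dose levels, FH by dose is a two-sample t test on change scores. At d = .42 with 55 v 55, SE = √(2/55) = 0.191 and power is 58.8%, against the stated figure of about 54%. A split of 37 v 73 gives 54.1%, but the document states no such split. The stated figure is near, but not reproduced under equal groups.

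**2. The three-way contrast.** Sex by FH by dose is a difference of differences of four cell means of change scores:

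- SE = √(4/27.5) = 0.381 SD, twice 0.191, on 110 − 4 = 106 df.
- 95% interval half-width = 1.983 × 0.381 = 0.756 SD; full width about 1.51 SD.
- Difference detectable with 80% power (noncentral t): 1.08 SD.

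**3. Miss rates per metric, FH effect in one sex and none in the other.** With equal numbers of men and women, a pooled effect d that arises wholly in one sex is 2d in that sex. So .42 pooled becomes 2 × .42 = .84, and .26 becomes 2 × .26 = .52.

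| Effect in one sex v other | Corresponds to | Noncentrality | Power | Missed |
|---|---|---|---|---|
| .84 v 0 | intensity, pooled .42 | .84/.381 = 2.20 | 58.8% | 41% |
| .52 v 0 | threshold/tolerance at the pooled upper bound .26 | .52/.381 = 1.36 | 27.2% | 73% |
| .42 v 0 | pooled average .21 | .42/.381 = 1.10 | 19.4% | 81% |

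A 40,000-run simulation of the .42 v 0 case also gave 19.4%. Because threshold and tolerance are stated as below .26, 73% is a lower limit for them.

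**4. Uneven FH groups.** With one-third FH+, power falls from 58.8% to 53.9% at .84 v 0, and from 19.4% to 17.7% at .42 v 0.

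**5. Can absence be shown?** To exclude a sex difference of 0.42 SD in both directions, the interval must lie between −0.42 and +0.42, a span of 0.84 SD. An interval 1.51 SD wide cannot fit, whatever the estimate.

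**The case against.** The strongest reply is that low power should not be overstated, and most of that reply stands. A reader might infer that an FH effect confined to one sex would be called absent about 80% of the time. The document does not support that as a general statement. Its d = .42 is pooled over the sexes, so putting .42 in one sex and 0 in the other halves the plan's own effect. At .84 v 0, consistent with the pooled figure, detection is more likely than not. The 81% belongs only to the .42 v 0 case, per metric.

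The rule also covers several metrics. With three uncorrected metrics, each at .42 in one sex, the chance that at least one is significant is about 34% to 48% (correlations .7 to 0), against 11% to 14% when there is no moderation at all. Missing on every metric is thus less frequent than 81%, though the extra chances also raise false positives. For relief ratings the pilot FH effect is d = .54; confined to one sex that is 1.08, which has about 80% power. Whether relief counts as a metric of analgesia is arguable, since the Aim 1 analysis lists it separately.

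Two points of wording also stand. The plan says the term will inform the question, not that it settles it. And a reader might infer that the sponsor will report no subgroup at risk after a null result; no section says so, and Aim 3 speaks only of what positive evidence may show. The plan is also open about limited power for FH by dose.

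None of this rescues the absence half of the rule. The interval width does not depend on which effect size is assumed, and no other criterion is attached to the question.

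**Conclusion.** The point holds in this form: the plan treats absence of a significant sex by FH by dose term as informative, gives no power or detectable difference for that term, and has a sample that cannot support a conclusion of absence. The interval is about ±0.76 SD, and 80% power needs about 1.08 SD. Under complete moderation consistent with the pooled pilot effects, the per-metric miss rate is about 41% for intensity and at least about 73% for threshold and tolerance; uneven FH groups make it slightly worse.

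These sizes rest on 110 completers and on three things the document does not state: an equal FH split, alpha .05 for these models, and change-score SD units. The pilot details are in a grant document that is not part of this text, so the SD unit of d = .42 cannot be confirmed.

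This is a cheap improvement. Empirical Question 1 is an open question without a directional hypothesis, and the change affects what may be concluded, not how the trial is run.

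**What to change.** In the Data Analysis Strategy for Aim 3, replace the presence-or-absence sentence with: *Empirical Question 1 will be informed by the estimated sex difference in the FH by dose effect with its 95% CI, and by the FH by dose effect within each sex with 95% CIs. A non-significant three-way term will be reported as inconclusive, not as absence of moderation.*

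In the Power Analysis, add that under equal cells the detectable sex difference in the FH by dose effect is about 1.08 change-score SD at 80% power, and that excluding a sex difference of 0.42 SD in both directions is not attainable with 110 completers. State the FH split and alpha assumed. An escape clause that permits a claim of absence if the interval excludes 0.42 SD in both directions should not be added, because it could never apply at this sample size.

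The cost is wording, plus one less favourable sensitivity figure. No participants, procedures or data are added.
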